3. STUDY DESIGN AND PROCEDURES

3.1 Overall study design and flow chart

This is a prospective, randomized, controlled, open clinical study with parallel-group design. A total of 70 young males with delayed or absent puberty will be randomized to receive hormone replacement during 6 or 12 months. The study includes 9 or 10 visits at the clinic during a total period of 12 months.

To not expose boys for a new treatment (Nebido and Puregon in group I and Nebido in group II) that is inferior to Stand of Care Testoviron, a fertility test will be performed after 10 evaluable patients in each arm in the groups.

The subjects will be divided to two groups depending on whether they have I) absences of puberty (n=30) or II) delayed/slow progress of puberty (n=40):

I) Boys with absence of puberty (testis 1-3 mL and morning testosterone less than 0.5nM) will be randomized to two alternative pubertal replacement therapies; 1) low dose of Testoviron Depot® (SoC) 50 mg i.m. injection once a month or 2) rhFSH (Puregon®) and low dose Nebido® (one injection of 200 mg every 3 months). Those randomized to receiving rhFSH (Puregon®) and low dose Nebido® will start both treatments concomitant. The rhFSH (Puregon®) dose will be adjusted to reach serum FSH levels of 3-5IU/ml (see appendix D). This is expected to happen within one month (first check after one week after start of treatment with Puregon) and if not reach within one month of start of Puregon treatment the patient will be withdrawn from the study. Boys who have been randomized to Puregon/Nebido but at inclusion have serum levels of FSH above 3 will not be treated with Puregon, but if the patient during the study on 2 concomitant visits have serum FSH below 3IU/L he will be treated with Puregon to achieve serum FSH levels 3-5 IU/L during the rest of the study (see appendix D). The treatment will continue for 12 months. The effect will be evaluated after 6 and 12 months respectively on the development of masculinization and on spontaneous start of puberty. If the spontaneous puberty has started, the pubertal hormone replacement treatment will be stopped. The Nebido treatment will be dose adjusted in patients after the 1st injection if the testosterone profile shows to high or low levels; the goal is to have similar levels during 2 months as in early puberty (1-3 nM). For individual Nebido® adjustments in group I see appendix D.

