5.1.1 Doses and treatment regimens

Lowest possible starting doses will be administrated.

Puregon® solution (rhFSH) for injection subcutaneously in ampoules of 300 IE/0.36 mL, will be administrated as multiple doses (3 times per week) to boys randomized to Puregon/Nebio who have serum FSH levels below 3 IU/L Group I. The first dose of Puregon will be given at the clinic under medical supervision to rule out any hypersensitivity reactions immediately after dosing. Otherwise it will be used and handled according to manufacturer instruction. Boys who at inclusion have serum levels of FSH above 3, but during the study on 2 concomitant visits have serum FSH below 3 IU/L will be offered to start Puregon treatment to achive serum FSH levels reached 3-6 IU/L during the rest of the study.

Nebido® a solution for injection 1000 mg/4mL and 200 mg or 250 mg will be administrated every 3rd month s. For patients on Nebido® in group I, an evaluation of the testosterone profile will be done

after the first injection and possibility to adjust the dose. For patients in group II an interim analysis on testosterone levels will be done after 4 patients in each group for the possibility to titrate up or down for the remaining study period. For Puregon® (rhFSH) dosing see appendix D

Group I: Individual dosing on the basis that the testosterone level should be between 2-4 nM during 8 of 12 weeks. The dose may be adjusted up or down with intervals of 50 mg.

Group II: A dose check will be made after the first 4 boys. If the testosterone levels are between 4-9 nM during 8 of 12 weeks, the dose may be adjusted up or down with intervals of 50 mg. See appendix D

The aim for Nebido® treatment is to have morning testosterone levels in the mid or upper early puberty range (1-3 nM) for boys with absence of puberty (group I) and the lower range of mid puberty (4-9 nmol/L) for boys with delayed puberty (Group II). See appendix D

Testoviron Depot® is given once a month intra muscular and the dose will be 50 mg in group I and 75 mg in group II (SoC; no dose adjustment).

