- a. The rhFSH (Puregon®) dose will be adjusted to reach serum FSH levels of 3.0 IU/mL or higher. The starting dose will be 50 IU. The FSH levels will be determined on visit 4. If serum FSH is lower than 3.0 IU/L the dose will be increased to 75 IU. If serum FSH are higher than 5.0 IU/L the dose will be reduced to 30 IU. Patients who have changed the Puregon® to 30IU or 75IU, an extra visit 7 -10 days after the change will be done to determine the serum FSH levels. For patients on 75IU Puregon® if serum FSH under 3.0 IU/L the Puregon® dose will be increased to 100IU and if serum FSH are higher than 5.0 the dose will be reduced to 50IU. For patients on 30IU Puregon® if serum FSH under 3.0 IU/L the Puregon® dose will be increased to 50IU and if serum FSH are higher than 5.0 the treatment with Puregon® will be stopped. If serum FSH in these patients are not 3.0 IU/mL or higher at visit 5, the patient will be taken out from the study.
- b. Dose adjustments of starting dos of Puregon® is possible after the first 5 patients for the rest of the study. If the serum FSH levels are less than 3.0 IU/L at visit 4 in 3 or more of 5 patient, the starting dose will be increased to 75IU for the remaining patients randomized to Puregon® and Nebido®.
- c. Boys who have been randomized to Puregon®/Nebido but at inclusion have serum levels of FSH above 3 will not be treated with Puregon®, but if the patient during the study on 2 concomitant visits have serum FSH below 3.0 IU/L will be treated with (Puregon®) as described above
- d. The Nebido treatment will be dose adjusted in patients after the first injection if the testosterone profile shows to high or low levels, the goal is to have the similar levels during 2 months as in early puberty (1-3 nM). If the serum testosterone level are less than 1.0 nM at visit 6, the dose will be increased to 250mg for the remaining part of the study. If the serum testosterone level is higher than 3.0 nM at visit 6, the dose will be decreased to 150mg.

II Boys with delayed/slow progress of puberty

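### Read literally, Appendix D I a stops Puregon for high FSH and then withdraws the same boy if his FSH is below 3.0 at visit 5 (minor, wrong as written)

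*SAP*

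**What the plan says.** All of this concerns group I, Puregon/Nebido arm.

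- **Who starts Puregon.** Section 5.1.1 gives it "to boys randomized to Puregon/Nebio who have serum FSH levels below 3 IU/L Group I".
- **Target.** Appendix D I a opens with a target FSH of 3.0 or higher, with no upper limit. Section 3.1 gives a range: the "dose will be adjusted to reach serum FSH levels of 3-5IU/ml". (The text mixes IU/mL and IU/L; IU/L is assumed here.)
- **Stepping down.** Under I a the starting dose is 50 IU and FSH is checked at visit 4. Above 5.0 the dose falls to 30 IU, with an extra check 7 to 10 days later. For a boy then on 30 IU, "if serum FSH are higher than 5.0 the treatment with Puregon® will be stopped".
- **Removal.** The sentence directly after that is: "If serum FSH in these patients are not 3.0 IU/mL or higher at visit 5, the patient will be taken out from the study".
- **Body text.** Section 3.1 expects the level to be reached within one month, and "if not reach within one month of start of Puregon treatment the patient will be withdrawn from the study".
- **Boys not on Puregon.** Under I c, boys in this arm who "at inclusion have serum levels of FSH above 3 will not be treated with Puregon" stay in the study. Two low values lead to Puregon being given, not to withdrawal.

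**The concern.** The stop rule and the removal rule stand side by side, and the second contains no exception for a boy who has just been handled under the first. Puregon is withdrawn from him because his FSH is too high. If his FSH then falls below 3.0, the printed words withdraw him because it is too low. He would leave the study because the dosing rule was followed, not because the treatment failed to raise his FSH.

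Removal at about month 1 comes before the 12-month LHRH test at visit 10, which gives the group I primary endpoint (sections 6.3 and 8). Section 4.6 has a discontinued boy seen if possible, but does not keep him for that test. The loss can arise in one arm only, because section 5.1.1 fixes the Testoviron dose without adjustment. Section 8 does not say how a removed boy enters the Fisher test.

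**Working it through.** The plan gives no figure on this point, so there is none to reproduce. The check sets the rules side by side and then does two short calculations.

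**1. Whom does the removal sentence cover?** Its subject can be read as the boys on 30 IU, named just before it, or as all boys whose dose was changed. The stopped boy belongs to both sets. A narrower reading, boys still on Puregon who stay below 3.0, is probably what was meant but is not written.

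**2. Can both rules reach the same boy?** Inputs: visit 4 at day 7 and visit 5 at 1 month (Table 1; taken as day 30); extra check 7 to 10 days after the dose change (Appendix D I a).

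- Dose changed on the day of sampling: stop on day 7 + (7 to 10) = day 14 to 17. Time off drug at visit 5: 30 − (14 to 17) = 13 to 16 days.
- Three days for each of the two FSH results (assumption; section 6.6.1.2 says only that analysis is prompt): 7 + 3 + (7 to 10) + 3 = day 20 to 23. Time off drug: 30 − (20 to 23) = 7 to 10 days.

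Either way the stop precedes visit 5, so both rules can apply.

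**3. Could his FSH be below 3.0 by then?** He started Puregon because FSH was below 3 IU/L (section 5.1.1). A return below 3.0 off drug is plausible but not certain: his own secretion may have risen, and the document gives no rate of decline.

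**4. Does another rule protect him?**

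- Section 3.1 withdraws a boy who does not reach the level. Its range is 3-5, and this boy's recorded values may go from below 3 to above 5 with none inside it. The section does not clearly remove him, but it does not exempt him either.
- Item I c is limited to boys with FSH above 3 at inclusion. He was below 3, so it does not apply.

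**5. Size if one boy is removed.** Inputs: 15 boys in the arm (section 4, Table 2) and an assumed number of successes if everyone is kept and observed. The 80% in section 8 rests on 16 of 20 in Appendix E and is not a group I figure, so 12/15 is an assumption; 9/15 is shown as a second one. The contrast is the boy kept versus the boy removed.

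| Assumed rate, all kept | Removed boy would have been | Excluded from analysis | Counted as failure |
|---|---|---|---|
| 12/15 = 80.0% | responder | 11/14 = 78.6% (−1.4 points) | 11/15 = 73.3% (−6.7) |
| 12/15 = 80.0% | non-responder | 12/14 = 85.7% (+5.7) | 12/15 = 80.0% (0) |
| 9/15 = 60.0% | responder | 8/14 = 57.1% (−2.9) | 8/15 = 53.3% (−6.7) |
| 9/15 = 60.0% | non-responder | 9/14 = 64.3% (+4.3) | 9/15 = 60.0% (0) |

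Under both assumptions the shift is between 0 and 6.7 points, and its direction depends on the boy's unobserved outcome and on how he is counted.

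**The case against.** The best defence is that the paragraph explains itself. Item I a opens with a target of 3.0 or higher, and the removal sentence repeats that threshold. Read together, the sentence is a failure criterion for boys whom Puregon could not raise. A boy above 5.0 at two checks has met the target, and a sensible investigator would not withdraw him.

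The path is also narrow. It needs FSH below 3 at entry, above 5.0 on 50 IU, still above 5.0 on 30 IU, and below 3.0 by visit 5. No rate is given for any step. Item I b allows the starting dose only to be raised, which suggests that the authors expected under-response. Nothing here touches the endpoint definition, the test, the margin or the sample size.

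Most of this stands, and it is why the point is minor. It does not remove the point. The intent has to be inferred, the printed words include the stopped boy, and two sites in an open trial could apply them differently.

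Two stronger readings are tempting.

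- A reader might measure the harm by the gap between excluding a removed boy and counting him as a failure, for example 11/14 − 11/15 = 5.2 points. That gap arises with any dropout. It is not the effect of this rule.
- A reader might see item I c as a direct contradiction of I a. It is not, because it covers a different set of boys. It shows only that low FSH off Puregon is not in itself treated as a reason to leave the arm.

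**Conclusion.** The wording is wrong as printed, and the defect is minor. Followed literally, Appendix D I a can withdraw a randomised boy for the expected result of a stop that the same paragraph ordered, although he had reached its target of 3.0 or higher on drug. The probable intent is narrower, but no rule in the document states it.

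The number affected is unknown and may be zero; the arm has 15 boys. For one boy, the effect on the arm's success rate is 0 to 6.7 points, given the assumed 12/15 (or 9/15). The timing rests on a 30-day month and on dose changes made on the sampling day or after an assumed 3-day delay for each result.

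A reader might infer that the group I comparison is materially biased, or that section 3.1's withdrawal of boys who do not reach the level is itself at fault. The document supports neither inference here: it gives no frequency for this path, and the correction leaves the withdrawal of boys who fail to reach 3.0 on Puregon in place.

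**What to change.** Replace the removal sentence in Appendix D I a along these lines:

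*A boy still receiving Puregon who has not reached serum FSH 3.0 IU/L at visit 5 is withdrawn. A boy whose Puregon was stopped for FSH above 5.0 IU/L is not withdrawn for a later value below 3.0 IU/L; he continues Nebido, has the 12-month LHRH test and is analysed as randomised.*

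The amendment should also say whether Puregon may be restarted in him after two low FSH values, as I c does for boys never started, and at what dose. Importing I c unchanged would send him back to the schedule that begins at 50 IU, which has already overshot in him. The restart dose should not exceed 30 IU, and since 30 IU also took him above 5.0, the sponsor should consider whether to go lower.

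Cost: a few sentences by amendment. No patients or scheduled visits are added for the 12-month test, which section 6.3 already plans at visit 10 for group I; a restart would need FSH checks. The downside is that some boys in the combination arm may spend part of the year on Nebido alone, as I c already allows.

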II) Boys with delayed/slow progress of puberty (testis 4-6 mL and morning testosterone less than 4 nM) will be randomized to receive either 1) Testoviron Depot® (SoC) 75 mg i.m. injection once a month (SoC) or 2) Nebido® one injection of 250 mg at start and after 3 month. The treatment will continue for 6 months, dose adjustments will be possible after the first 4 patients on Nebido® (250 mg) for the rest of the study. The aim for the Nebido® treatment is to have morning testosterone levels in the lower range of mid puberty (4-9 nmol/L). An interim analysis has to be done after the first 5 patients and thereafter keep or adjust the dose (see appendix D for adjustment of the Nebido® dose for group II). The treatment will be evaluated after 6 month on development of masculinization and on spontaneous start of puberty after 12 months.

Figure 1 and Table 1 show the study overview and activities.

Figure 1a Study design Group I (absence of puberty)

[figure not shown]

Figure 1b Study design Group II (delayed puberty)

[figure not shown]

Table 1 Study activities

	Visit 1	Visit 2	Visit 3	Visit 4	Visit 5	Visit 6	Visit 7	Visit 8	Visit 9*	Visit 10
	Pre-	0	2 days	7 days	1 month	2 months	3 months	6 months	9* months	12 months
Informed consent	X									
Demography	X									
Medical history	X									
Nicotine use	X									
Weight, height	X						X	X	X	X
Pulse, blood pressure	X									
Physical exam	X									
Bone-age	X									
LHRH test	X									X*
Pubertal stage	X						X	X	X	X
HQOL	X							X		X
Hb, liver enzymes	X						X	X		X
LH, FSH	X	X		X*	X		X	X	X	X
DHEAS,		X						X		X
Incl/excl criteria		X								
Study drug		X								
Testosterone, estradiol		X	X	X	X	X	X	X		X

SHBG, AMH, InhibinB		X			X			X		X
Signs of masculinization								X		X
Plasma for masspektometri of steroids	X							X		X
Adverse events	X	X	X	X	X	X	X	X	X	X
Serious Adverse event recording	X	---	---	---	---	---	---	---	---	---

*Visit 9: Group I only

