6.6.1.4 Testosterone and Estrogen

Venous blood for testosterone (2.5 mL) and estrogen (5 mL) analysis will be drawn at visits 2, 3, 4, 5, 6, 7, 8 and 10, centrifuged, frozen and sent to tillväxtlab at Drottning Silvias barn- och ungdomsjukhus; Sahlgrenska University/Östra, Göteborg and stored in -20° C for later analysis.

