- a. Dose adjustments of Nebido® is possible after the first 5 patients on Nebido® (250 mg) for the rest of the study. The aim for the Nebido® treatment is to have testosterone levels in the lower range of mid puberty (4-9 nmol/L) during 2 months. An interim analysis will be done after the first 5 patients and thereafter keep or adjust the dose for the remaining study. If the serum testosterone level are less than 4.0 nM at visit 6 in 3 or more of 5 patient, the dose will be increased

to 300 mg for the remaining patients randomized to Nebido®. If the serum testosterone level are higher than 9.0 nM at visit Y in 2 or more in 5 patient, the dose will be decreased to 200 mg for the remaining patients randomized to Nebido®.

Study protocol Appendix E - Statistiska beräkningar

p2	nOK, gl drog	nOK, ny drog	p1		p1-p2	$p1*(1-p1)/n1$	$p2*(1-p2)/20$	under rot	rot
0,8	16	17	0,85		0,05	0,006375	0,008	0,014375	0,119896
0,8	16	16	0,8		0	0,008	0,008	0,016	0,126491
0,8	16	15	0,75		-0,05	0,009375	0,008	0,017375	0,131814
0,8	16	14	0,7		-0,1	0,0105	0,008	0,0185	0,136015
0,8	16	13	0,65		-0,15	0,011375	0,008	0,019375	0,139194
0,8	16	12	0,6		-0,2	0,012	0,008	0,02	0,141421

p2 %"lyckade" i testoviron gruppen
 p1 %"lyckade" i grupp med ny behandling

16 pojkar måste "lyckas" i den nya behandlingen, dvs lika många som antas "lyckas" efter den gamla behandlingen för inte den nya behandlingen ska betraktas som inferior, dvs 25% färre lyckade med nya drogen

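### The Nebido titration rules are inconsistent: Appendix D II a cites a visit Y that does not exist, and section 5.1.1 conflicts with Appendix D on the Group I band and the Group II check

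*SAP*

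**What the plan says.** Section 3.1 sends the reader to Appendix D for both groups: "adjustments in group I see appendix D" and, for Group II, "see appendix D for adjustment of the Nebido". Section 5.1.1 also refers to it.

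**Group II, Appendix D II a.** The starting dose is 250 mg and the target 4-9 nmol/L. The dose for later boys goes up to 300 mg on this condition: "If the serum testosterone level are less than 4.0 nM at visit 6 in 3 or more of 5 patient". It goes down to 200 mg on this one: "If the serum testosterone level are higher than 9.0 nM at visit Y in 2 or more in 5 patient". The check comes after the first 5 patients. Section 3.1 allows adjustment after 4 patients and then requires the interim look after 5. Section 5.1.1 twice says 4. Section 5.1.1 also makes levels between 4 and 9 nM the condition under which the dose may be moved.

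**Group I.** Section 5.1.1 states: "Group I: Individual dosing on the basis that the testosterone level should be between 2-4 nM during 8 of 12 weeks". Later, the same section gives the aim as "morning testosterone levels in the mid or upper early puberty range (1-3 nM) for boys with absence of puberty (group I". Section 3.1 and Appendix D I d also use 1-3 nM. Appendix D I d reads a single value at visit 6: below 1.0 nM the dose rises from 200 to 250 mg, and above 3.0 nM it falls to 150 mg.

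**The concern.** These thresholds decide the dose given, so a contradiction between them can change treatment. The Group II trigger with the undefined visit is the one that protects against high exposure. Section 1.4 lists the harms of high testosterone (aggressiveness, acne, a rise in haemoglobin, and possibly reduced growth through early closure of the growth zones) and offers monitoring with dose adjustment as the safeguard. The study is open (section 3.2) and has no safety committee (section 7.1.5), so a gap in the rule would be filled case by case.

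The rules also define the treatment under test. Testoviron is not adjusted (section 5.1.1); only the Nebido arms are. In Group II a single decision fixes the dose for the boys who follow, and that dose is then compared with Testoviron in the non-inferiority reading of section 8.

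**Working it through.** The plan gives no figure for this rule that could be reproduced. The check sets the texts side by side and adds simple counting.

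**1. Which visit is Y?** Table 1 (section 3.1) numbers visits 1 to 10. On testosterone and estrogen sampling, section 6.6.1.4 says "analysis will be drawn at visits 2, 3, 4, 5, 6, 7, 8 and 10". After the first injection (visit 2) and up to month 3 (visit 7, when the next injection is due), that leaves visits 3, 4, 5, 6 and 7. The other Nebido testosterone triggers in Appendix D (both Group I thresholds and the Group II raising rule) use visit 6, which is month 2. The stated aim is to hold the level for 2 months. Visit 6 fits best, but nothing in the text says so.

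**2. Group I bands.** For a boy whose level stays in one range:

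| Level (nM) | Appendix D I d | Section 5.1.1 (band 2-4) |
|---|---|---|
| below 1 | raise to 250 mg | below band, may rise to 250 mg |
| 1-2 | keep 200 mg | below band, may rise to 250 mg |
| 2-3 | keep 200 mg | in band, 200 mg |
| 3-4 | cut to 150 mg | in band, 200 mg |
| above 4 | cut to 150 mg | above band, may fall to 150 mg |

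The sections disagree at 1-2 and at 3-4 nM. The gap is one 50 mg step, and 50/200 = 25% of the starting dose. Fifteen boys are planned for this arm (Table 2).

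**3. Size of the Group II check.** The triggers are counts out of 5. If the check is made after 4 boys, exactly 2 low values or exactly 1 high value leaves the outcome depending on a fifth boy who has not been read.

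**4. Group II condition in 5.1.1.** Read literally, it allows adjustment when levels are already in the 4-9 nM target. Appendix D acts only below 4.0 or above 9.0 nM. A lost 'not' is the obvious explanation.

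**5. Reach of the Group II decision.** Table 2 plans 20 boys on Nebido: 20 - 5 = 15 later boys at most. Visit 6 is two months after the first injection, and nothing pauses recruitment while the results are awaited, so boys enrolled meanwhile would already have started on 250 mg.

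**6. Both Group II triggers at once (minor).** Since 3 + 2 = 5, both can be met at one visit, but only by exactly 3 low, 2 high and none in range. With independent boys, the probability is 10 × pL³ × pH², where pL and pH are the chances of a low and a high value. The plan gives neither, so these are assumptions:

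- (0.2, 0.2): 10 × 0.008 × 0.04 = 0.003
- (0.3, 0.3): 10 × 0.027 × 0.09 = 0.024
- (0.4, 0.3): 10 × 0.064 × 0.09 = 0.058
- (0.6, 0.4), the maximum, with no boy in range: 10 × 0.216 × 0.16 = 0.346

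If visit Y were a different visit, the same boy could count for both rules and a clash would be easier to reach. The two answers are 300 and 200 mg, 100 mg apart, or 100/250 = 40% of the starting dose. No precedence is given.

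**7. Puregon (minor).** The FSH target is 3-5 IU/L in section 3.1 but 3-6 IU/L in 5.1.1 for boys who start Puregon late. The highest dose is 75 IE in Table 3 but 100 IU in Appendix D I a.

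**The case against.** The other side is strong on several points.

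- **Visit 6 is close to obvious.** All the sibling triggers use it. This stands as the best reading. It is not certain, because a check for high levels could sensibly be placed at an earlier, peak-level visit, so the sponsor should confirm.
- **Appendix D is the working rule.** Section 3.1 points there, and the 2-4 nM band appears only once against 1-3 nM everywhere else. This largely stands. But no sentence says that Appendix D prevails, and 5.1.1 keeps its own numbers.
- **The Group I comparison mixes two kinds of rule.** Section 5.1.1 is permissive and looks at 8 of 12 weeks, whereas Appendix D takes one visit 6 value. This stands: two readers could dose the same boy 50 mg apart, not that they would.
- **The joint trigger is rare.** This stands for a single visit at moderate rates, and a check after 4 boys could not produce it at one visit at all (3 + 2 exceeds 4).
- **The study is described as hypothesis-generating, and no primary test is touched.** True, and it limits the weight of the point. It does not make contradictory dosing thresholds acceptable.

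**Conclusion.** The Nebido titration rules contradict each other and should be corrected. The firm parts are the undefined visit in the Group II lowering trigger, the 2-4 against 1-3 nM band in Group I, the check after 4 against 5 boys, and the Group II condition in 5.1.1 that permits adjustment within target. The Group II decision reaches at most 15 of 20 boys. The Group I conflict is up to 50 mg (25% of the starting dose) for a boy who stays at 1-2 or 3-4 nM. Starting doses are fixed, so the defect is confined to the titration rules.

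Four stronger readings are tempting and not supported:

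- A reader might infer that the lowering rule is unusable. It has a natural reading, visit 6; what is missing is confirmation.
- A reader might infer that the two Group II triggers are likely to collide. At one visit this needs the exact 3 low, 2 high split, and the probabilities above rest on assumed rates.
- A reader might infer that all 15 later boys will be affected. That is an upper bound.
- A reader might infer that the sample size, error rate or primary test is compromised. The plan ties none of these to the dose rule.

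**What to change.** Amend the wording as follows:

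1. State that Appendix D governs Nebido and Puregon adjustment, and remove the competing numbers from sections 3.1 and 5.1.1.
2. In Appendix D II a, replace visit Y with visit 6, once the sponsor confirms that this was intended.
3. Set the Group II check after 5 boys throughout, and act only on levels outside 4-9 nM.
4. In section 5.1.1, use 1-3 nM for Group I.
5. Add one sentence saying which dose applies if both Group II triggers are met. The sponsor should choose. Keeping 250 mg is possible, but lowering fits at least as well: the plan sets a lower count for reducing (2) than for raising (3), and section 1.4 stresses the harms of high levels.
6. Align the FSH target (3-5 or 3-6 IU/L) and the Puregon maximum (75 or 100 IU) across section 3.1, section 5.1.1, Table 3 and Appendix D.

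The cost is one protocol amendment, with Ethics Committee approval and, if applicable, regulatory approval before use (section 9.5). It needs no extra visits, samples or boys.
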